**Optimizing PrEP Uptake and Adherence among Male Sex Workers Using a Two-Stage Randomization Design**  
**December 3, 2018**  
**Site Principal Investigator: [name]**

## **OBJECTIVE**

The objective of this study is to evaluate the effectiveness of the “PrEPare for Work” intervention, consisting of strength-based case management and cognitive behavioral theory-based PrEP adherence counseling, in promoting PrEP uptake and adherence among men who have sex with men (MSM) in Providence, RI.

## **BACKGROUND**

Male sex workers (MSW), or men who exchange sex for money, goods, drugs, or other items of value with other men, are at exceptionally high risk for HIV infection. A recently published meta-analysis from the PIs for this application found an estimated HIV prevalence of 20% among men who have ever engaged in transactional sex in the United States (US) [1]. Research shows that MSW, particularly those who solicit male clients on the street, engage in frequent condomless anal sex with both paying and non-paying sexual partners [2,3]. Notably, MSW have a higher burden of psychosocial problems, such as heavy substance use, depression, and victimization, and often face unique contextual challenges such as homelessness and unemployment—all of which potentiate HIV sexual risk. Additionally, while MSW are often included as a subgroup of MSM, survey data show that a large proportion (approximately 50%) identify as heterosexual [4]. As such, behavioral interventions to decrease HIV risk specific to gay- or bisexual-identified men often do not reach MSW and do not adequately address their lived realities. Moreover, compared to cisgender and transgender women who engage in transactional sex, MSW are less likely to identify as “sex workers” [5]; as a result, even interventions or programs specific to sex workers may not be appropriate. Hence, HIV prevention interventions addressing the unique life circumstances of MSWs are needed to curb HIV spread.

A growing number of clinical trials and demonstration projects have provided strong evidence for the efficacy of a once-daily oral pill (emtricitabine/tenofovir) as pre-exposure prophylaxis (PrEP) for the prevention of HIV among uninfected, at-risk individuals, including MSM [6–8] and injection drug users [9]. However, implementation of PrEP in at-risk populations such as MSWs has been limited by several concerns including adherence to the medication. In order to be most effective, PrEP adherence must be high (four or more doses per week) [10,11]. A body of evidence regarding adherence to PrEP is just beginning to emerge, suggesting that, similar to antiretroviral therapy (ART) among HIV-infected individuals, PrEP adherence may be suboptimal among individuals with psychosocial problems (e.g., substance use, depression, violence victimization). Given the complexity of sexual decision making for MSW, a PrEP uptake and adherence package would need to be responsive and tailored to MSWs’ distinct circumstances and contextual surroundings to optimize their likelihood of initiating PrEP, and sufficiently adhering to, this biomedical HIV prevention modality. Informed by our formative research (including individual qualitative interviews, focus groups, and a longitudinal epidemiological cohort study of HIV risk, in which all examined perceived PrEP acceptability) and programmatic work with US based MSWs over the past decade, we adapted the “Life-Steps” model [12,13]—a proven efficacious intervention for HIV treatment adherence among marginalized groups—for the provision of PrEP. The resulting theory-based intervention, PrEPare for Work—developed by our interdisciplinary investigator team—addresses access to and uptake of PrEP, and provides skills training to optimize adherence. As such, the PrEPare for Work intervention includes two components: 1) Strength-based case management for PrEP access and initiation, and 2) Cognitive-behavioral theory-based PrEP adherence counseling by a trained masters-level counselor—both as part of a comprehensive, context-specific approach to HIV prevention for MSW in Providence, Rhode Island. Providence, often described as the epicenter of male sex work, has one of the largest populations of street-based MSWs in the US [4].

## **STUDY SITES**

**Project Weber**, a 501(c)(3) nonprofit organization serving MSWs in Rhode Island, is the primary recruitment and screening site for this study. In over seven years of service, Project Weber has reached over 800 MSWs, with 160 individuals currently accessing its drop-in center. The study team published a sexual health needs assessment of MSWs in Providence, Rhode Island in collaboration with Project Weber [4]. Most needs assessment participants reported a history of HIV testing within the past year (73%). Self-reported HIV prevalence was 6%, and 22% reported Hepatitis C infection. Most participants had been engaged in sex work for more than 3 years (70%), and more than a quarter (26%) reported unprotected anal and/or vaginal sex with sex work clients. Of 48 participants reporting drug use patterns, most (94%) had used drugs in the past, 39% had previously injected drugs (25% in the past month), and 19% reported sharing needles. Nearly half (42%) reported a previous diagnosis of depression. These results demonstrate both the study team's success in engaging this population and the ongoing and the complex HIV prevention needs experienced by this population. Project Weber staff will conduct screening assessments at the drop in center and during routine outreach services to identify potential research participants. Eligible participants will be referred to Brown research staff for eligibility confirmation. The case management visits may occur at this site and will be administered in one on one sessions. Additionally, survey and adherence counseling sessions may be conducted at Project Weber, if preferred by the participants.

**Brown University** is the home institution of Principal Investigators [name] and [name]. Brown University will act as the coordinating site for all regulatory matters (protocol and SOP authoring; IRB applications and approvals; Quality Control and Assurance; etc.). Brown University will also collaborate in the design, implementation, and analysis of the study, including primary responsibility for epidemiologic and statistical analysis of study data. Additionally, survey and adherence counseling sessions may be conducted at Brown University School of Public Health, if preferred by the participants (including collection of blood and hair for drug level testing).

**The Miriam Hospital** (TMH) will collaborate with Brown University for study implementation, and is the home of Principal Investigator [name]. The PrEP clinic at TMH will be the primary study site for clinical visits. Participants will complete an initial visit at TMH PrEP clinic during which time they will be screened for eligibility for PrEP, and this site will serve as the site for follow-up PrEP monitoring visits, including where HIV and renal function tests will occur, as well as collection of blood and hair for drug level testing. Additionally, survey and adherence counseling sessions may be conducted at The Miriam Hospital, if preferred by the participants.

## RESEARCH PROTOCOL

**Specific Aim 1 - Pilot RCT:** To evaluate both PrEP initiation and adherence, we will use a two-stage randomization design. In Stage 1, we plan to enroll 130 MSW (65 per randomization arm to achieve N=104 completers for Stage 1; ~80% retention), who will be equally randomized to receive either the PrEPare for Work strength-based case management (SBCM) or standard of care (i.e., referrals only) to evaluate successful PrEP initiation. In Stage 2, those who initiate PrEP (n~44; ~80% in Stage 1 intervention arm and ~20% in Stage 1 comparison arm), regardless of their Stage 1 randomization condition, will then be equally randomized to the PrEPare for Work adherence intervention condition or standard of care comparison condition (22 per randomization arm to achieve N=40 completers for Stage 2; ~90% retention). While we are aware that there may be important differences that affect adherence in those who initiate PrEP without additional SBCM and those who received SBCM, we anticipate that randomization at the second stage will balance out potential confounding by level of motivation to initiate PrEP. See point of contact diagram below for specific details.

**Recruitment:** All participants will be identified by staff at Project Weber, our community partner organization and study site for this study, and will live in or participate in sex work in RI. In addition to identifying participants at the drop-in center, participants will be recruited from a variety of sources: (1) members of our recruitment/outreach team will actively recruit participants in the community via direct outreach at venues where we know sex workers solicit clients (such as bars, night/dance clubs, on the streets), (2) via the internet, by posting study related advertisements which may include a brief anonymous self-administered pre-eligibility assessment, (3) via direct engagement with internet escorts on the internet for which

their profiles are soliciting sex for pay, and (4) via snowball techniques. These efforts have been successful in other projects with this population, and as such, we do not anticipate having problems reaching our target sample. However, if we are not able to reach our sample size with these methods, we will also enroll MSWs in Greater Boston (<1 hour from Providence) and implement the intervention at Fenway Health—the largest provider of medical services for, and research with, MSM in New England, including PrEP ([name] & [name] both have faculty appointments at Fenway Health and having ongoing research studies there). Eligibility screening may be incentivized with a \$5 gift card in order to maximize recruitment in this difficult-to-reach population in particular venues (such as bathhouses). This initial screening incentive will be provided for completion of the eligibility survey, regardless of whether the participant is actually eligible after screening.

**Screening and Enrollment:** As part of the screening process, a brief anonymous pre-eligibility assessment may be conducted online or by phone prior to the full eligibility screening. The full eligibility screening may take place by phone, in a private room at one of the study sites (Brown University, Project Weber or The Miriam Hospital); or in a public location (coffee shop, library, etc) where the participant feels most comfortable. Participants will be asked to complete a survey assessing demographic information, sexual orientation, ethnic/racial identity, education level, history of HIV and other STDs, history of HIV testing, access to HIV and STD diagnostic and treatment services, recent sexual behavior, characteristics of recent partners, use of PEP previously and knowledge and anticipated acceptability of PrEP and other new biomedical prevention methods. The screening visit will take place in a private room at one of the study sites (Brown University, Project Weber or The Miriam Hospital); the participant can select where he feels most comfortable. Enrollment will be limited to participants who are English -speaking, HIV-uninfected, report having exchanged sex for money or drugs with another man in the past three months in RI, report at least one episode of condomless anal intercourse with an HIV-infected or unknown serostatus partner in the previous three months, who express an interest in using PrEP as an HIV prevention tool and live in the New England area. Potential participants will be asked to undergo antibody testing for HIV as well as screening for Hepatitis B infection (Hepatitis B surface antigen and antibody) and renal insufficiency (serum creatinine). Individuals will also be screened for acute HIV infection. A release of medical information will be requested upon enrollment. Only information regarding the PrEP clinic visit is requested and completion of the release is voluntary.

**Research Assessments:** Behavioral assessments will be conducted using ACASI at Stage 1 baseline, Stage 1 one-month follow-up, Stage 1 two-month follow-up, Stage 2 baseline, and Stage 2 three and six-month follow-up visits. It is expected that each ACASI survey will require less than 1 hour to complete. Both quantitative and qualitative assessment will collect information on the following key domains: sexual behavior; risk for HIV/STI transmission; use of alcohol and drugs; depression and anxiety; knowledge, attitudes, and beliefs related to pre-exposure prophylaxis. Exit interviews will be conducted as individual interviews and will last 15-20 minutes. Research assessments can be conducted at The Miriam Hospital, Brown University or Project Weber. Visits that include collection of blood and hair may only occur at The Miriam Hospital or Brown University. Participants who are unable to complete the Stage 2 three- or six-month follow-up visit in-person at Brown University or The Miriam Hospital may be given the option to schedule a phone interview with research staff to complete the Stage 2 follow-up assessment. This option will only be offered in extenuating circumstances (ex. participant moves out of the state). Phone interview follow-ups will be interviewer-administered. Participants who complete the phone interview will then receive instructions with a labeled, prepaid FedEx envelope to provide a self-collected hair sample. The sample will be mailed back to Brown University.

**Incentives:** All participants may receive up to \$210. Participants will receive \$30 USD compensation at each assessment visit (Stage 1 baseline, Stage 1 one-month follow up, Stage 1 two-month follow-up, Stage 2 baseline, Stage 2 three-month follow up and Stage 2 six-month follow up), individuals randomized to the strength based case management intervention condition will receive \$15 USD for the first case management session and individuals randomized to the Stage 2 intervention condition will also receive \$15 USD

compensation for each of the PrEPare for Work intervention sessions attended. Participants who complete a phone interview follow-up will receive a \$15 gift card upon completion of the interviewer-administered assessment and an additional \$15 gift card once the participant's hair sample is received via FedEx. Study staff will confirm the mailing address with participants prior to sending the gift cards.

Overview of the PrEPare for Work PrEP Initiation and Adherence Intervention Package (see appendix for manual).

1. Stage 1: Strengths-based Case Management to facilitate integration into The Miriam Hospital PrEP Clinic. Following Stage 1 randomization, participants randomized into the intervention arm will be provided a case manager to support, facilitate, and assist in linkage to our established PrEP clinic at The Miriam Hospital and to facilitate initiation of, and obtaining, PrEP medications. This is comprised of facilitated strengths-based case management to assess barriers to initiation, to help navigate the PrEP medical care system and to support the participant and health care staff in meeting the challenges faced with obtaining PrEP medication (e.g., overcoming insurance barriers, or barriers with copays). This also includes facilitated integration into the PrEP clinic and obtaining their PrEP prescription through the clinic (refilled monthly).

A trained staff member will be based at Project Weber and will provide case management to all eligible participants interested in taking PrEP. Staff will receive training concerning the provision of case management services, including how to use past experiences with sex work as a tool for understanding, role modeling, outreach and engagement, ethical guidelines, such as confidentiality and professional boundaries, and administrative tasks (e.g., documentation).

2. Stage 2. Only participants who complete an initial visit at the PrEP clinic are clinically evaluated, receive a prescription for PrEP, and confirm their interest in using PrEP for HIV prevention will be randomized in Stage 2 to either the PrEPare for Work adherence training and counseling condition or the standard of care condition. All participants enrolled in Stage 2 will be offered a study cell phone to receive appointment reminders and, for participants randomized to the intervention, to receive daily adherence SMS text reminders (full description on page 6 under Adequacy of Protection of Risk). Participants may choose to decline the study cell phone and/or to participate in the daily adherence SMS text reminders (full description SMS text component page four Section B). For participants who decline and elect to use a personnel cell phone for study appointment reminders and/or daily adherence SMS text messages standard text messaging rates will apply and are not compensated for by the study.

A. *Component I. Individual Adherence Counseling for PrEP adherence among MSW in Providence, RI.* Intervention participants will undergo up to three adherence training and counseling intervention sessions (once per week for 2-3 weeks) with a clinical interventionist. Intervention sessions may be scheduled once a participant is assigned to the intervention and must be completed within 12 weeks of randomization. A summary of topics to be covered is as follows:

- i. *Introduction, rapport building, education.* The initial adherence session will involve getting to know the participant, a conversation about general information about PrEP, and the rationale for the counseling. This will include a general discussion of the participant's sexual behavior, sexual history, and general patterns regarding unsafe sex.
- ii. *Educational information about PrEP and coping with side effects*
- iii. *Motivation for using PrEP, based on motivational counseling principles*
- iv. *HIV risk reduction counseling and behavioral adjustment*
- v. *PrEP adherence and problem solving barriers to adherence.* The remaining time will involve going through a list ("steps") of potential barriers to PrEP adherence. The following list of topics will be addressed, although the relative emphasis on the different topic areas will be adjusted according to the unique needs of the participants.
  - a. Daily schedule and weekend schedule, for the purpose of scheduling dosing
  - b. Coping with distress; mental health referrals made as necessary

- c. Substance use, including possible interaction with PrEP adherence; referrals for substance treatment and support services made as necessary
  - d. Sex work and daily adherence
  - e. Other structural factors, e.g. homelessness or other barriers, as appropriate
  - f. Reminder strategies for taking PrEP
- B. *Component II. Daily SMS text messaging of personalized reminders to take PrEP as prescribed (“reminder cues”)*. As an optional component, we will send daily text messages to all participants randomized to the PrEPare for Work intervention condition, as reminders to take PrEP as prescribed and as cues regarding behavioral skills gained as a result of in person adherence counseling sessions. The messages will not have any information about the participant’s health, medication or any information identifying them as a MSW. Text messages will be programmed to begin upon completion of the stage two baseline and to end upon the completion of the three-month follow-up visit. Participation in text message reminders will be left to the participants’ discretion, may be deployed on a study cell phone or a personal cell phone, and can be stopped at any time. Text messages will be programmed utilizing a web-based data management system. This system is password protected and available only to trained study personnel. Text messages are registered by participant ID and study cell phone number. Participants personal information cannot be traced back to study cell phones. Participants electing to use personal cell phones to receive text reminders will be registered by name and phone number to eliminate identifying the study ID with a personal phone number.

**Data management:** Demographic and behavioral assessments will be administered primarily on a tablet computer using a web-based data collection tool system. As the participant enters data points, each response will be immediately encrypted and transmitted back to a secure server. This will enhance confidentiality and minimize risks to patients. The digital data collection tool will be programmed to automatically store identifiable information and any PHI in a separate database from questions about demographics, risk behaviors, and health outcomes. No data will be stored on the tablet computer at any time.

Whenever possible, the information will be collected digitally in this manner. However, in venues with large testing volume, or when the PIs deem it safer to collect data in paper format, a paper survey will be administered. In these cases, hard copies of the survey will separate any identifying information from health outcome data. Identifying information including name, phone number and zip code will be stored with their unique identifier separately from all other responses and will serve as a linkage file. The unique identifier will be used on all other testing and data collection documents. The linkage file will be kept only on secure and encrypted Lifespan and Brown University computers.

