Statistical Analysis Plan

September 15, 2015

Optimizing PrEP Uptake & Adherence Among Male Sex Workers (MSW)
Using a 2-stage Randomization Design
(NCT03086057)

Specific Aim 2: Pilot RCT. Initially, the distribution of all variables will be assessed, as will the autocorrelations across time between all study variables and the primary outcomes. Dependent variables will be examined to determine which distributional models are most appropriate for subsequent statistical procedures. We will examine the equivalence of the random assignment of groups with regards to key baseline characteristics, including socio-demographics and sexual risk-related variables. In the unlikely event that randomization does not work to balance these characteristics at baseline, we will assess whether baseline differences may account for differences in outcomes. Attrition effects will be evaluated by testing whether systematic differences exist between those participants who complete the research versus those who drop out. In this way, we can determine the nature of the potential bias introduced by attrition from the study.

Primary Analysis. The primary analysis for Stage 1 will compare PrEP initiation at 1-month post Stage 1 randomization between the study arms. For stage 2, the primary analysis will compare adherence (defined by percent of drug in blood) at the 3 and 6 month visits between the study arms. Changes in self-reported adherence, sexual behavior adjustment and substance use will also be examined. Moreover, group differences in number of PrEP clinic appointments kept will be compared. All analyses will use two-tailed tests of significance, with significance at alpha = 0.05. We will use generalized linear models (GLM) with properly-chosen link functions to analyze longitudinal data for each analysis. The GLMs will be estimated using generalized estimating equations with robust standard error estimates (GEE)^{67,68}, which provides an extension of regression analysis to the case of correlated or repeated observations and allows for inclusion of both categorical and count dependent variables and for appropriate modeling of covariance structures when observations are correlated across time. We will follow an intent-to-treat model, analyzing participants in the study arm to which they were assigned, regardless of fidelity to assigned group.

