Power and Sample Size Considerations. As a pilot study, the primary emphasis is on feasibility of the two arms and hence power is limited; and to find statistical significance, the effect sizes would need to be large. However, the number of repeated measures does increase power for the longitudinal analyses. For stage 1, proportion of participants in each condition who initiate PrEP, with a two-tailed p-value of 0.05, and 53 participants per arm, we would need at least a 30 percentage point difference across the two conditions (e.g., if 20% of the comparison arm and 50% of the intervention arm initiated PrEP) to achieve 80% power. For stage 2, percent adherence since the last visit will be assessed yielding 3 repeated blood-drug levels across baseline, 3, and 6. With a two-tailed p-value of 0.05, group sample sizes of 22 participants per arm, assuming a correlation of 0.80 between repeated adherence measures and with up to 10% attrition there will be greater than 80% power to detect in excess of a medium effect size difference (approximately 10% in the slope) between the intervention and comparison groups. For categorical outcomes (e.g. percent of patients in each condition achieving at least 90% adherence via blood drug levels), with a two-tailed p-value of 0.05, the three repeated measures, and 22 patients per arm, we would need at least a 25 percentage point difference across the two conditions (e.g., if 50% of the comparison arm and 75% of the intervention arm had at least 90% adherence) to achieve 80% power.

Missing Data. We will assess for patterns of missing data, which are expected to be low as the study utilizes A-CASI. We will explore strategies for imputing missing data based on patterns of missingness and apply appropriate techniques, applying sensitivity analysis to determine the optimal method of handling the missingness⁷¹⁻⁷³.

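### The Stage 2 comparison of adherence levels in about 44 people names no Stage 1 arm term; prespecifying one is a cheap improvement whose gain depends on a gap the documents do not size

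*Protocol*

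**What the plan says.** The protocol (Research Protocol, Specific Aim 1) re-randomizes PrEP initiators 1:1 without regard to their Stage 1 arm. It gives the source of this group as "those who initiate PrEP (n~44; ~80% in Stage 1 intervention arm and ~20% in Stage 1 comparison arm", with 22 per arm and 40 expected completers. It concedes that people who initiated with case management and people who initiated without it may differ in ways that matter for adherence, and then states that "we anticipate that randomization at the second stage will balance out potential confounding by level of motivation to initiate PrEP".

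The SAP's opening paragraph (Specific Aim 2: Pilot RCT) adds a balance check: "We will examine the equivalence of the random assignment of groups with regards to key baseline characteristics, including socio-demographics and sexual risk-related variables". If imbalance is found, "we will assess whether baseline differences may account for differences in outcomes". For Stage 2, the Primary Analysis paragraph says that "the primary analysis will compare adherence (defined by percent of drug in blood) at the 3 and 6 month visits between the study arms", using models "estimated using generalized estimating equations with robust standard error estimates". No covariate is named and no small-sample correction is mentioned. The moderator paragraph allows exploratory interactions but lists no moderators.

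Neither document, as available, names Stage 1 arm as a stratification factor or a model term for Stage 2. The point-of-contact diagram to which the protocol refers is not shown, so it could not be checked.

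**The concern.** The protocol identifies a plausible prognostic factor and relies on one randomization of about 44 people to neutralize it. Randomization does so in expectation, but in a single trial of this size the roughly 9 comparison-arm initiators can easily fall unevenly. If Stage 1 arm predicts adherence, an uneven split shifts the unadjusted difference in levels, and variation from that source stays in the error term.

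The balance check is a weak remedy. Its examples are socio-demographic and sexual risk variables, it has no stated threshold, and it leads to no stated model. What is at stake is power in the levels comparison, and discretion over whether and how to adjust once balance has been seen. The validity of the test is not at stake.

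**Working it through.** **Inputs from the documents.** About 44 people, 22 per arm; 40 completers (protocol, Specific Aim 1). Stage 1 mix 80:20, hence about 35 and 9 (32 and 8 among completers). Two-sided alpha 0.05, correlation 0.80 between repeated measures, up to 10% attrition (SAP).

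**Assumptions.** The adherence gap between Stage 1 arms among initiators is not given; 0 to 1 SD is used. Outcomes are continuous and complete. Effects are in single-visit SDs unless stated.

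**1. The plan's own power figure.** The SAP claims more than 80% power for more than a medium effect, expressed as a slope. The detectable effect is (1.96 + 0.84) × √(2v/n), where v is the variance factor at correlation 0.80.
- Slope, baseline to 6 months: v = 2(1 − 0.80) = 0.40. With n = 20 this gives 2.80 × 0.20 = 0.56 SD, which agrees with the SAP if medium means 0.5 SD.
- Mean level at 3 and 6 months: v = (1 + 0.80)/2 = 0.90. This gives 2.80 × 0.30 = 0.84 SD.

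The levels comparison therefore has little precision to spare.

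**2. Chance imbalance** (hypergeometric, 22 per arm, 9 comparison-arm initiators).

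| Split of the 9 | Probability of this or worse | Shift in unadjusted difference | Fisher p |
|---|---|---|---|
| 6:3 | 45.7% | 3/22 = 0.14 × gap | 0.46 |
| 7:2 | 13.2% | 5/22 = 0.23 × gap | 0.13 |
| 8:1 | 2.1% | 7/22 = 0.32 × gap | 0.02 |

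If the balance check is a 5% test (an assumption; the SAP does not say), it flags only 8:1 or worse. A 7:2 split would pass. With 40 completers and 8 from the comparison arm, 6:2 or worse has probability 23.5% (shift 0.20 × gap), and only 7:1 or worse (4.4%) is flagged.

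**3. Break-even gap** (in SDs of the participant mean). With q = 9/44, omitting the term multiplies the variance by 1 + q(1 − q) × gap² × 44/43 = 1 + 0.166 × gap². Including it multiplies the variance by 1.025 on average. These are equal at gap = √(0.025/0.166) = 0.39. At a gap of 1 the ratio is 1.166/1.025 = 1.138, equivalent to 44 × 1.138 = 50 people, or about 6 more.

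**4. Power for levels by simulation.** With an exchangeable working correlation and balanced data, the GEE estimate equals least squares on participant means (variance 0.90), and the Kauermann-Carroll correction equals HC2. The effect, 0.82 SD for 44 people and 0.86 SD for 40, was set to give 80% power with no gap. Corrected standard errors and a t reference were used.

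| n | Gap | Never adjust | Adjust only if flagged at 5% | Always adjust |
|---|---|---|---|---|
| 44 | 0 | 80.0% | 79.9% | 79.0% |
| 44 | 0.5 SD | 78.0% | 77.9% | 78.8% |
| 44 | 1 SD | 73.2% | 73.4% | 79.1% |
| 40 | 0 | 79.9% | 79.7% | 78.8% |
| 40 | 0.5 SD | 78.2% | 78.1% | 79.0% |
| 40 | 1 SD | 73.3% | 73.5% | 78.8% |

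At 0.4 SD, never and always adjusting give 78.8% and 78.9% (n = 44), in line with step 3. Check-then-adjust triggers in only 2 to 4% of trials, so it recovers almost none of the loss.

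**5. Type I error.** Uncorrected robust errors give 6.0–6.5% without the term and 6.5–6.9% with it. Corrected errors give 4.8–5.2% and 4.9–5.3%.

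**6. Where the gain disappears** (n = 40).
- Baseline drug level in the model and already carrying the whole gap: 84.6% falls to 83.5% at 0.5 SD, and 84.1% to 83.7% at 1 SD.
- Baseline drug level in the model, but the gap arises only after baseline: 79.1% rises to 83.7% at 0.5 SD.
- Slope contrast with a constant gap: a main effect changes nothing, and a Stage 1 arm-by-time term takes power from 80.4% to 79.1%. If the gap grows by 0.5 SD over follow-up, that term raises power from 76.1% to 78.9%.

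**The case against.** The strongest reply is that nothing here is an error. Independent 1:1 randomization does balance Stage 1 arm in expectation, leaving out a prognostic covariate is a legitimate choice, and the SAP says that "the primary emphasis is on feasibility of the two arms and hence power is limited". The benefit also rests on a gap that no document sizes. Between 0 and 0.5 SD the change is within about one point either way, and the 5 to 6 point gain needs a gap larger than the 0.82 SD treatment effect assumed in the calculation. The SAP's power statement concerns a slope, on which a constant gap cancels. The list in the balance check is not exhaustive, and the 5% rule is supplied here, not by the SAP. The small-sample correction addresses a problem that exists without any Stage 1 term. Under a logit link for the binary adherence outcome, adjustment would change the estimand from a marginal to a conditional odds ratio.

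Most of this stands as a limit on the point, and it is why the recommendation is modest and confined to the continuous levels comparison. It does not remove the point. The stated primary analysis is a comparison of levels; the protocol itself raises the difference; an unlisted exploratory moderator is not a main effect in the primary model; and a check without a rule leaves the decision on adjustment until after balance is seen.

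**Conclusion.** The point holds as a modest improvement in precision, with medium confidence. The Stage 2 randomization keeps the unadjusted test valid, and the balance check does not harm type I error. Over the range considered the trade favours the term: about 1 point of power lost at no gap, 5 to 6 gained at 1 SD.

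The result is not sensitive to the mix. If initiation were 50% and 20%, as in the SAP's Stage 1 power example, about 31 and 13 of the 44 would come from the two arms. Power at a gap of 1 would then rise from 72.6% to 79.5% (noncentral t, effect 0.87, both in SDs of the participant mean). The conclusion rests on the assumed gap and effect sizes, a continuous outcome, the SAP's correlation of 0.80, and a levels contrast in which no baseline drug level already carries the gap.

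**What to change.** Before Stage 2 outcomes are examined by arm, add to the SAP:

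> Stage 1 arm will be a main effect in the Stage 2 GEE comparison of adherence levels at 3 and 6 months, whether or not imbalance is seen. Robust standard errors will use a small-sample correction (Kauermann-Carroll) with a t reference distribution.

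If the slope is to be the primary contrast, the term must be Stage 1 arm-by-time. If outcomes have already been seen by arm, report the adjusted model as a labelled post hoc sensitivity analysis. Stratifying Stage 2 allocation by Stage 1 arm is optional, and only possible if allocation has not started.

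**Cost.** One degree of freedom (two with the time interaction), and about 1 point of power if Stage 1 arm is unrelated to adherence. Without the correction, the term would add 0.3 to 0.5 point of type I error. The correction lowers nominal power by about 3 to 4 points (82.8% to 80.0% unadjusted, no gap, n = 44), which is the price of bringing an error rate of about 6.5% back to the stated 5%. Stage 1 arm is already known for everyone, so no new data, visits or staff are needed.
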